1.2 Primary Study Endpoints

The primary outcome of interest is change in fibrinolysis as measured by PAI-1 level immediately following completion of the exercise and nutritional counseling program.

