1.3 Secondary Study Endpoints

Secondary Outcomes are as follows: (1) Change in PAI-1 after 16-week exercise regimen; (2) Change in other markers of hemostasis [von Willebrand Factor (vWF), P-selection, Protein S, Protein C, Factor VII, Factor VIII, Fibrinogen, Antithrombin,] after 16-week exercise regimen; (3) Change in PAI-1 stratified by PNPLA3 genotype after 16-week exercise regimen; (4) Correlation between loss of hepatic fat as measured by magnetic resonance imaging proton density fat fractionation (MRI-PDFF) and changes in hemostatic markers after 16-week exercise regimen; (5) Correlation between maximal oxygen consumption (VO₂ max) and hemostatic markers after 16-weeks of exercise; (6) health-related quality of life (HRQOL) change following exercise intervention

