Exercise Medicine Unit or the Hershey Center for Applied Research. Aerobic exercise can be completed on either the treadmill, exercise bike, rowing machine or the elliptical machine. Subjects will be given the opportunity to complete these supervised sessions virtually or in-person as described above. If the subject chooses to complete the strength training sessions virtually, the study EP will schedule and complete exercise sessions using Penn State HIPAA complaint Zoom. Additional home exercise beyond the recommended sessions will be assessed by downloading data from the Fitbit Charge2. Review of downloaded information will take place once a week. Any subject who performs <3 sessions in any given week during the 16-week study period will be required to extend their training by two additional weeks to offset loss of physical conditioning. They can be extended no longer than 4 weeks. If subject misses more than 2 weeks of exercise sessions, they will be discontinued from the study.

Weekly review of dietary logs obtained via self-report through the FitBit application and secure web-based platform with directed feedback by trained study personnel (nutritionist) will also be provided either in-person, telephone interview or video chat. Additionally, participants will be given dietary education forms. In the event that the subject does not self-report their dietary intake through the FitBit platform, the 24-hour dietary recall data collection form will be utilized.

Study investigators will perform an interim history and physical examination on a monthly basis during the exercise protocol. If subject is required to extend protocol, interim history and physical examinations will continued to be performed on a monthly basis. The subject may complete these either in person or virtually.

The purpose of the post-exercise program liver biopsy is to observe changes in stage of fibrosis and NASH Activity Score. Liver biopsy is the gold standard to stage chronic liver disease from NASH and the benefit of disease staging and prognostication outweighs the small risk to the subject. Non-invasive methods of diseases staging (serologic scoring systems NFS, FIB-4) and ultrasound with elastography have inferior performance characteristics with much lower sensitivity and specificity and are hindered by significant inaccuracy with misclassification bias observed in upwards of 25%.(1, 93) Sub-

[REDACTED]

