| Day/Week | Day 0 | Weeks 0-4 | Weeks 5-19 | Week 20 |
| Initial comprehensive history and physical exam | X | | | |
| Focused history and physical exam | | | X (monthly) | X |
| Anthropometric assessment | X | | X (monthly) | X |
| Physical activity questionnaire (IPAQ) | X | | X (monthly) | X |
| Dietary Log | | X (weekly) | X (weekly) | x |
| FitBit activity data download | | X (weekly) | X (weekly) | X |
| Cardiopulmonary fitness testing (VO2 max) | X | | | X |
| Electrocardiogram (ECG) | X | | | |
| Laboratories | X | | | X |
| Stool sample | X | | | X |
| Urine pregnancy testing (if applicable) | X | | | |
| Genetic testing | X | | | |

| | | | | |
|---|---|--|-------------|-----------------------|
| Liver MRI-PDFF | X | | | X |
| PROMIS Quality of Life Assessment via iPad (completed under direct supervision of trained research personnel) | X | | X (monthly) | X |
| DXA body composition testing | X | | | X |
| Liver biopsy | | | | X (if sub-randomized) |

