8.2 Sample size determination
Subjects will be randomized into two treatment groups. This is an efficient study design with increased power and is appropriate for the proposed exercise intervention. The primary outcome will be change in PAI-1 following a 16-week exercise course. Secondary outcomes are described above. Baseline levels of PAI-1 are between 35-45 ng/mL.(72, 74-76) Estimates for change in PAI-1 following exercise regimens of between 3-8 months duration range between 23-37% with >30% reduction only reported in regimens >6 months long.(72, 74-76) De Gues *et al.*(75) found an initial 24.5% reduction as measured at four months in PAI-1 levels in thirty healthy adults aerobically exercising 2.5 hours per week. We expect the exercise intervention to result in a 23% reduction (9 ng/dL) in PAI-1. We expect no change in PAI-1 levels in the control arm. We conservatively determined power calculations utilizing the standard deviations in the literature (2.0 for no exercise group and 14.0 for the aerobic exercise group). We expect a 15-20% attrition rate;(94) to account for this we will enroll an additional six subjects.

Based on these assumptions and a 2:1 enrollment ratio with two subjects in the aerobic exercise arm to every one subject in the standard of care arm, a total study enrollment size of 28 subjects in the aerobic exercise arm and 14 in the standard of care arm will achieve 80.74% power to detect a difference in mean PAI-1 at sixteen weeks of at least 9 ng/mL, using a two-sided, two-sample unequal variance t-test with a significance level (alpha) of 0.05. A total study enrollment of **42 subjects** is planned.

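### The date of the primary PAI-1 draw is not fixed, and if it follows programme completion, exercise subjects who miss sessions can be sampled up to 4 weeks later than controls

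*Combined protocol and SAP*

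**What the plan says.** The current text describes the timing of the primary PAI-1 sample in three ways.

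- **Sixteen weeks.** Section 8.2 states "The primary outcome will be change in PAI-1 following a 16-week exercise course" and gives the power to "detect a difference in mean PAI-1 at sixteen weeks of at least 9 ng/mL". The follow-up paragraph of 7.2 also puts the final assessments directly after the 16-week intervention.
- **Week 20.** The schedule in 7.2 covers both arms. Its columns are Day 0, Weeks 0-4, and then "Weeks 5-19 | Week 20". Laboratories are marked at Day 0 and Week 20 only. Section 7.3 gives participation as 20 weeks, and section 14.0 ties a stipend to a week 20 visit.
- **Programme completion.** Section 1.2 defines the endpoint as "change in fibrinolysis as measured by PAI-1 level immediately following completion of the exercise and nutritional counseling program", with no week attached.

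Section 1.3 lists as a secondary endpoint "1) Change in PAI-1 after 16-week exercise regimen", although only one post-baseline draw exists to serve both it and the primary.

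The programme length can also vary. Sections 3.3.1 and 7.2 add two weeks of training for a subject with fewer than three sessions in a week. Section 7.2 adds a cap: "They can be extended no longer than 4 weeks". It also keeps the monthly examinations going for a subject whose protocol is extended. Controls are asked not to change how active they are. For withdrawn subjects, 3.3.2 promises follow-up at the same time points and gives a phone call as its example.

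**The concern.** A randomized comparison of a biomarker needs both arms measured on the same clock. Here the clock can depend on two things that arise after randomization: the arm, because only one arm has sessions to miss, and adherence, because only subjects who miss sessions are extended. If the draw waits for the extension, the least adherent exercise subjects receive additional training weeks before their primary outcome is measured, and controls are not shifted to match. That sits badly with the intention-to-treat analysis promised in 3.3.2 and 8.3.

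There is a practical side too. With no fixed date and no visit window, site staff would have to settle the timing of the primary sample subject by subject in a trial of 42.

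**Working it through.** **1. The plan's own figure, and whether timing enters it.** Inputs from 8.2: difference 9 ng/mL, SD 14.0 (exercise) and 2.0 (control), unequal-variance t-test, two-sided alpha 0.05, stated power 80.74%.

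- With 22 and 11 evaluable subjects: SE = √(14²/22 + 2²/11) = √(8.909 + 0.364) = 3.045; Satterthwaite df = 22.67; noncentrality = 9/3.045 = 2.96; power from the noncentral t = 80.74%. This matches the plan.
- With 28 and 14, the same formula gives SE = 2.699 and power 89.66%.

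So the stated power belongs to 33 evaluable subjects, which is a separate matter. What matters here is that the week of sampling is not an input. Fixing the time point changes no sample-size figure.

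**2. Can sixteen weeks and week 20 be the same visit?** Section 7.2 has a lead-in of four weeks but does not say whether it lies inside the 16 weeks or before them.

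- Lead-in before the course: 4 + 16 = 20, which agrees with the Week 20 visit.
- Lead-in inside the course: training ends at week 16, and the only post-baseline draw comes 20 − 16 = 4 weeks later. That does not fit the immediate sampling required by 1.2.

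The schedule does not decide it. Weeks 5 to 19 are 19 − 5 + 1 = 15 weeks, or 16 if Week 20 is counted. Subjects already train during the lead-in, so the text does not decide it either.

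**3. Programme end, by extension.** Each extension is 2 weeks, to a maximum of 4.

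| Reading | No extension | +2 weeks | +4 weeks |
|---|---|---|---|
| 16 weeks counted from Day 0 | week 16 | week 18 | week 20 |
| Four-week lead-in, then 16 weeks | week 20 | week 22 | week 24 |

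A control has no exercise programme to complete and stays in the first column. If the draw follows completion, the lag behind controls is 0, 2 or 4 weeks on either reading. If Week 20 is one calendar date for everyone, the lag is 0 on either reading. No passage says which of these applies.

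**4. Who can be shifted.** The extension rule speaks of any subject, but it stands in the description of the exercise arm (and in the removal criteria of 3.3.1), and its trigger counts training sessions. Controls have none, so in practice it reaches only the exercise arm.

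**5. Size of the effect on PAI-1.** A figure would need the proportion extended, the course of PAI-1 over the weeks in question, and the effect of the missed sessions. The documents give none of these. The literature summary in 8.2 says reductions "range between 23-37% with >30% reduction only reported in regimens >6 months long", which compares different studies and is not a week-by-week curve. No number follows.

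**The case against.** The best defence is that there is little conflict. A four-week lead-in plus 16 weeks is 20. The schedule labels Week 20 as the end of the exercise programme, and 7.3 and 14.0 agree with it. No passage says that the laboratory draw moves with an extension. The plan expects no change in controls, so under its own assumption the date of the control draw adds nothing to the difference. The extension is meant to make up lost training, so its net effect could be nil or of either sign. Measuring at completion is also a coherent efficacy endpoint.

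Much of this stands, and it rules out three stronger readings.

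- A reader might infer that the plan has no sample at sixteen weeks at all. That holds only if sixteen weeks is counted from Day 0, which the text does not require.
- A reader might infer that extended subjects will be drawn at weeks 22 to 24. That needs the lead-in to precede the course and the draw to move with the extension. Neither is stated.
- A reader might draw a line from the 24.5% reduction at four months in one cited study to the reductions above 30% in regimens longer than six months, and read off a gain per extra week. The second figure is a boundary across other studies, and an extended subject has missed sessions, so the documents do not support such a slope.

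What the defence does not remove is the gap itself. The sum 4 + 16 is never written down. Even if it is granted, 1.2 and the follow-up paragraph of 7.2 tie the sample to completion, and 7.2 treats participation as longer for extended subjects. The expected absence of change in controls does not help either, because it is the exercise subjects who would be measured after a different length of time.

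**Conclusion.** The point holds in a limited form. The primary draw has three descriptions, and no rule says whether it moves with an extension. On the completion wording, outcome timing can differ between arms by 0 to 4 weeks, with the delay confined to exercise subjects who missed sessions. On a fixed Week 20 reading there is no difference. The conclusion rests on reading the extension rule as applying only where there are sessions to miss.

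No bias has been shown. Its size and direction cannot be computed from the documents, and the power calculation is untouched. The plan should still be changed, because the choice affects the primary comparison and can be settled at little cost before the data are seen.

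**What to change.** In 1.2 and 8.2, define the primary endpoint as change in PAI-1 from baseline to one fixed week after randomization, using the Week 20 visit already in the schedule. State the date from which weeks are counted, since the schedule starts at the initial assessment, and give the same visit window to both arms. Draw the sample at that week in every randomized subject, whether extended, withdrawn or neither. Section 3.3.2 should name this draw, because a phone call yields no PAI-1 value. Make any end-of-extension measurement secondary and optional, and say how secondary endpoint 1 in 1.3 differs from the primary, or remove it.

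Sections 3.3.1, 7.1, 7.2 and the schedule must be reconciled on whether the lead-in lies inside the 16 weeks, how long the programme is, and how an extension relates to the final visit. This can be done without altering the exercise rule, and no view is taken here on what that rule should be.

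The cost is mainly wording, plus the effort of bringing withdrawn subjects back for a blood draw. The downside is that an extended subject may have the primary draw before the extension ends. It may then be separated from that subject's end-of-programme MRI-PDFF and VO₂ max, which secondary endpoints 4 and 5 relate to the hemostatic markers, unless those are done at the same visit. An optional later draw would be an added procedure.

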8.3 Statistical methods
Subjects will be compared across multiple important baseline demographic, laboratory, imaging and histologic data. Results will be expressed as means with standard deviations. Chi-squared and Fisher's exact test will be used to analyze our categorical endpoints. Student's t test and Mann-Whitney Rank Sum test will be used for secondary analysis of differences in numerical lab data. Paired t-tests will be used where appropriate (e.g. comparison of pre- and post-intervention fibrosis parameters such as NFS or FIB-4 Score). A p value of <0.05 will be significant. Intention to treat analysis will be performed. Analyses will be conducted using SAS version 9.4. Multivariable regression models will be constructed.

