7.0 Study Design and Procedures

7.1 Study Design

The aims of this research proposal are to better understand the potential for lifestyle interventions to reduce the elevated clot risk of patients with NASH without needing to take an anticoagulant (e.g. warfarin, low-molecular weight heparin). This proposal includes a RCT to determine the efficacy of supervised exercise on future clot risk. A RCT (n=42) of subjects with NASH will be conducted with a supervised 16-week moderate intensity aerobic exercise program as the intervention and the effect on fibrinolysis will be measured by change in PAI-1.

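### Section 8.3 names no primary test and, as written, puts change in PAI-1 under Student's t or Mann-Whitney, whereas 8.2 powers it on Welch; under 8.2's SDs Student's t would be conservative and lose 21 to 26 points of power

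*Combined protocol and SAP*

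**What the plan says.** **Primary outcome.** Three sections describe it as a change. Section 1.2 has "change in fibrinolysis as measured by PAI-1 level immediately following completion of the exercise and nutritional counseling program", section 7.1 says "the effect on fibrinolysis will be measured by change in PAI-1", and section 8.2 says "The primary outcome will be change in PAI-1 following a 16-week exercise course".

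**Sample size (8.2).** The SDs are "2.0 for no exercise group and 14.0 for the aerobic exercise group", allocation is 2:1 in favour of exercise, and the power statement is made "using a two-sided, two-sample unequal variance t-test with a significance level (alpha) of 0.05". Stated power is 80.74% with 28 and 14 enrolled. The powered quantity is worded as a "difference in mean PAI-1 at sixteen weeks of at least 9 ng/mL, using a two-sided, two-sample unequal variance t-test", which reads as a follow-up level, not a change.

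**Secondary outcomes (1.3).** The first item is "1) Change in PAI-1 after 16-week exercise regimen", the same variable as the primary.

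**Statistical methods (8.3).** No test is named for the primary outcome. For laboratory values the section says that Student's "t test and Mann-Whitney Rank Sum test will be used for secondary analysis of differences in numerical lab data". It does not mention the unequal-variance test and gives no rule for choosing between the two tests it does name. Paired t-tests are reserved for pre/post comparisons where appropriate.

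**Schedule (7.2).** Laboratory tests are drawn at Day 0 and Week 20 only, so each subject has one post-baseline PAI-1 value.

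**The concern.** PAI-1 is a numeric laboratory value and its change is listed as a secondary outcome, so an analyst following 8.3 literally would run Student's t or Mann-Whitney on a variable that 8.2 plans to test by Welch. Student's t pools the two variances. With 2:1 allocation and the much larger SD assumed in the larger arm, pooling carries the exercise-arm variance into the control mean and makes the standard error too large. The two tests would then often disagree on the same data. In a trial of 42 subjects designed for about 81% power, the reader should not have to guess which result counts.

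**Working it through.** **Inputs.** From 8.2: difference 9 ng/mL, no expected change in control, SD 14.0 (exercise) and 2.0 (control), two-sided alpha 0.05, 28 and 14 enrolled, attrition 15–20%, six extra subjects. Assumption: Student's t means the pooled-variance test, which is the usual meaning, although 8.3 does not say so.

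**Step 1: reproduce 80.74%.** Welch standard error is √(s₁²/n₁ + s₂²/n₂), with Satterthwaite degrees of freedom and power from the noncentral t.

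- 28/14: √(196/28 + 4/14) = √7.286 = 2.699; power 89.7%. This does not match.
- 22/11: √(196/22 + 4/11) = √(8.909 + 0.364) = 3.045; df = 9.273² / (8.909²/21 + 0.364²/10) = 22.7; power 80.74%. This matches exactly.

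The pair 22/11 is not printed in the plan. It fits 20% attrition: 22/0.8 = 27.5, rounded up to 28, and 11/0.8 = 13.75, rounded up to 14. Taking the six extra subjects literally gives 42 − 6 = 36, or 24/12, where Welch power is 84.3%.

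**Step 2: Student's standard error.** Pooled variance is [(n₁−1)s₁² + (n₂−1)s₂²]/(n₁+n₂−2).

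- 22/11: (21×196 + 10×4)/31 = 134.1; SE = √[134.1 × (1/22 + 1/11)] = 4.28, against 3.05 for Welch (ratio 1.40).
- 28/14: (27×196 + 13×4)/40 = 133.6; SE = √[133.6 × (1/28 + 1/14)] = 3.78, against 2.70 (ratio 1.40).

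Roughly, at 22/11 Student's t needs an observed difference of 2.04 × 4.28 = 8.7 ng/mL for significance, nearly the whole design difference. Welch needs 2.07 × 3.05 = 6.3.

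**Step 3: size and power at SDs 14 and 2.** Simulation with normal data, 2,000,000 replicates per t-test cell. Welch size is 5.0% throughout.

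| Evaluable | Student size | Student power | Welch power |
|---|---|---|---|
| 22/11 | 0.9% | 55% | 81% |
| 24/12 | 0.9% | 60% | 84% |
| 28/14 | 0.9% | 69% | 90% |

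Mann-Whitney, the other test in 8.3, has size about 3.8% and power about 62% at 22/11, 67% at 24/12 and 74% at 28/14 (20,000 replicates). It lies between the two t-tests.

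**Step 4: how far the two t-tests disagree.** With a true difference of 9 and SDs 14 and 2, Welch is significant and Student's t is not in 26% of trials at 22/11 and 21% at 28/14. The reverse essentially never occurs.

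**Step 5: sensitivity to the control SD (22/11, exercise SD 14).**

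| Control SD | Student size | Student power | Welch power |
|---|---|---|---|
| 2 | 0.9% | 55% | 81% |
| 7 | 1.9% | 49% | 66% |
| 10 | 3.1% | 45% | 53% |
| 14 | 5.0% | 39% | 38% |

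**The case against.** **PAI-1 already has its test.** Section 8.2 names the unequal-variance test, and with one post-baseline draw secondary outcome (1) most plausibly repeats the primary. It could also mean within-arm change, to be tested by a paired t-test, where pooling across arms does not arise. This stands as a limit on the consequence. A reader might infer that the primary analysis has 55% power, or that the chance of missing a true 9 ng/mL effect rises from 19% to 45%. The documents do not support that: it would be so only if Student's t decided the PAI-1 conclusion. What remains is that 8.2 names Welch only within a power statement, while the analysis section omits it and its wording reaches a listed PAI-1 outcome.

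**Student's t may be loose wording.** Section 8.3 never says pooled or equal variance, and 8.2 shows that the authors allowed for unequal variances. This is fair, and it is why the figures are conditional. One sentence in 8.3 would settle it.

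**Mann-Whitney is also allowed.** True, so 55% is not the only power obtainable under 8.3. But Mann-Whitney also falls short of Welch here, and the plan gives no rule for choosing between it and Student's t.

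**The SDs may be closer than 14 and 2.** Then the gap narrows and disappears at equality. These are nevertheless the plan's own inputs.

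**Conclusion.** The point holds as an inconsistency between 8.2 and 8.3 on one variable, change in PAI-1. Applied under 8.2's SDs, Student's t would have a true size of about 0.9% and would lose 26 points of power at 22/11, about 25 at 24/12 and 21 at 28/14. This rests on the 14.0 and 2.0 SDs, normal data, the pooled form of Student's t, and arm sizes that are inferred for 22/11.

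Three stronger inferences are not supported:

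- **Excess false positives.** The larger SD is in the larger arm, so the error is conservative.
- **The same loss for the other laboratory markers.** The documents give no SDs for them, so no error is shown there.
- **A specific loss of power from the week-16 wording in 8.2.** With randomisation, change and level have the same expected difference. The plan neither says whether its SDs describe change or level nor gives a baseline SD, so no power figure follows. Welch on change remains the natural reading.

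**What to change.** 1. In 8.3, add: *Every between-arm comparison of change in PAI-1, primary or secondary, uses the two-sided Welch t-test specified in 8.2, at alpha 0.05. Mann-Whitney is a sensitivity analysis only.*
2. In 8.2, express the powered quantity as the between-arm difference in mean change in PAI-1.
3. In 1.3, delete secondary outcome (1) if it duplicates the primary. If a within-arm change is meant, say so.

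Optionally, use Welch for the other numeric laboratory values too. That is a low-cost choice, not the correction of a demonstrated error.

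**Cost.** Wording only, with no added subjects or data. If the SDs prove equal, Welch gives up about 1 point of power: 38% against 39% at 22/11 and 47% against 48% at 28/14, both SDs 14.

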7.2 Study Procedures

Subjects will be invited for initial consultation performed by the study PI. This will be completed at the GCRC. If subjects are not currently in the Penn State system, they will be registered prior to this consultation through the Penn State Gastroenterology/Hepatology clinic staff ([name] or [name]). For all individuals who provide signed, informed consent, the following baseline measures will be completed:

- Comprehensive history and physical examination
- Anthropometric assessment [height, weight, BMI calculation]
- Physical activity questionnaire (IPAQ)
- Urine Pregnancy Test
- Nutrition counseling will be provided by a Registered Dietitian (RD) to promote a hypocaloric, low-fat dietary intake pattern. In the case that Dietitians are unavailable in person, counseling will be completed by phone or video chat using the Penn State Health-branded Zoom. Food Frequency Questionnaire (FFQ) will be used to assess their current dietary practices. Individual caloric needs will be calculated at baseline using the Mifflin St. Jeor equation, providing resting energy expenditure (REE), multiplied by the appropriate activity factor (AF) to yield total energy expenditure (TEE). Adjusted body weight (ABW) will be used when the participant's BMI is equal to or greater than 30. Five-hundred to 750 calories will be subtracted to promote an approximate weight loss of 1 pound per week for participants whose BMI classifies as overweight or obese. Macronutrient distribution will be recommended at 50-60% carbohydrate, 15-20% protein, and 20-30% fat with <10% total calories attributable to saturated fat. A sodium intake of <2,000 mg daily will be encouraged.

ABW & IBW Calculations:

- Use ABW to calculate REE when BMI ≥ 30
 - ABW calculation:
 - Males: $IBW + 0.38 \times (BW - IBW)$
 - Females: $IBW + 0.32 \times (BW - IBW)$
 - IBW calculation:
 - Males = $106 + 6 \times (Ht.(in)-60)$
 - Females = $100 + 5 \times (Ht.(in)-60)$

REE via Mifflin St. Jeor Equation:

- Male: $10(wt. (kg)) + 6.25(ht. (cm)) - 5(age (yr)) + 5 = REE \times AF = TEE$
- Female: $10(wt. (kg)) + 6.25(ht. (cm)) - 5(age (yr)) - 161 = REE \times AF = TEE$

| Activity Factors: | |
|--|--|
| Lifestyle and Physical Activity Level (PAL) | |

| | |
|--|---------------------|
| Seated work with no option of moving around and little or no strenuous leisure activity | 1.4-1.5 |

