Whole blood will be drawn in the Penn State Hershey GCRC (hours 730a-4p) by trained GCRC nursing or NASHFit research staff. Whole blood will be obtained and placed into the following tubes in the amounts described below [total nine teaspoons (tsp) of blood]:

- Three 3mL lavender (EDTA) top tubes (1.8 tsp)
- Two 4.5mL green (sodium heparin) top tubes (1.8 tsp)
- Three 6mL red top tube (3.6 tsp)
- Three 2.7mL blue (sodium citrate) top tubes (1.6 tsp)

Samples will then be delivered by NashFit study personnel to both the Clinical Laboratory for processing to serum and platelet poor plasma and also to [name] in the Institute for Personalized Medicine (IPM) for processing prior to transfer to the Endocrine Core Laboratory. Samples will be frozen and picked up from the Clinical Laboratories by IPM staff and brought to the IPM for storage and also the Genome Sciences and Bioinformatics Core for Taqman assay performance. Coded samples will be shipped through the IPM to [name], Associate Professor in University Park for metabolomics analysis. Results will be sent back to the IPM per standard IPM operating procedure. Stool samples will be obtained from the subject at home with a home collection kit and mailed directly from the subject to [name] (collaborator), Assistant Professor of Medicine, Juniata College. Stool samples will be processed, analyzed with 16S rRNA testing and stored in [name] laboratory.

Intervention Conditions: The aerobic exercise protocol is adapted from the landmark NASH-exercise trials by Sullivan *et al*(91) and Bacchi *et al*(92) that demonstrated the efficacy of exercise in improving intrahepatic fat and body composition but did not evaluate the effect on hemostasis and thrombosis risk. Once subjects have passed screening, they will be randomized 2:1 into either the exercise or control group respectively (two exercise subjects per one control subject) using a computer-generated randomized scheme in blocks of six by an independent statistician ([name] Public Health Sciences).

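### Section 8.3 gives a pre/post paired t-test as its example analysis for NFS and FIB-4 and does not explicitly assign these scores a between-arm comparison

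*Combined protocol and SAP*

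**What the plan says.** The combined protocol and SAP describes a randomized trial with a concurrent control. Under section 7.2, "they will be randomized 2:1 into either the exercise or control group respectively (two exercise subjects per one control subject". Section 8.2 plans "a total study enrollment size of 28 subjects in the aerobic exercise arm and 14 in the standard of care arm".

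Section 8.3 contains three statements that could bear on the non-invasive fibrosis scores:

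- The only one that names them: "Paired t-tests will be used where appropriate (e.g. comparison of pre- and post-intervention fibrosis parameters such as NFS or FIB-4 Score".
- The sentence just before it, which is general: "Student's t test and Mann-Whitney Rank Sum test will be used for secondary analysis of differences in numerical lab data".
- A later sentence with no outcome, treatment term or covariate: "Multivariable regression models will be constructed".

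The threshold in the same section is "A p value of <0.05 will be significant".

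NFS and FIB-4 are listed in section 7.2 among the baseline calculations. They do not appear among the endpoints in sections 1.2 and 1.3. The schedule of assessments places laboratories at Day 0 and Week 20.

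Section 7.2 also lists, among the measures for all who sign consent, "Nutrition counseling will be provided by a Registered Dietitian (RD) to promote a hypocaloric, low-fat dietary intake pattern".

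**The concern.** A paired t-test asks whether a score changed over the study period. It does not ask whether the change differed by randomized arm. Whether it is run in each arm, in the exercise arm only, or over all subjects together, the control group is not the comparator. A significant result would therefore mix any exercise effect with time, regression to the mean, and the effect of counseling given outside the exercise program.

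The 2:1 allocation adds a second difficulty if the test is run arm by arm. With twice as many subjects, the exercise arm is more likely to reach significance for the same true change. Significant with exercise but not in controls can then look like a treatment effect when there is none.

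What is at stake is the reading of the fibrosis results. Section 2.1 says it is not known whether exercise improves fibrosis, and post-program biopsy is confined to a sub-study of ten subjects (section 7.2). NFS and FIB-4 are thus the fibrosis measures that could be compared across the two full arms, and a significant pre/post fall could be taken for new evidence.

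**Working it through.** **The plan's own figure.** The documents state no power, SD or expected change for NFS or FIB-4. The only power statement, in section 8.2, concerns PAI-1: the design "will achieve 80.74% power to detect a difference in mean PAI-1 at sixteen weeks of at least 9 ng/mL". It uses a two-sided unequal-variance t-test with SDs of 14.0 (exercise) and 2.0 (control).

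- Formula: SE = √(14²/n₁ + 2²/n₂), noncentrality = 9/SE, Satterthwaite degrees of freedom, two-sided alpha 0.05.
- At 22/11: SE = √(8.909 + 0.364) = 3.045, noncentrality 2.96, df 22.7, power 80.74%.
- At 28/14: SE = √(7.000 + 0.286) = 2.699, noncentrality 3.33, df 29.1, power 89.66%.

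So the figure reproduces for 33 evaluable subjects (33/0.80 = 41.25, rounded up to 42) rather than for 28/14 as worded. That is a separate matter. What counts here is that the PAI-1 comparison is between arms, so the paired-test question does not touch it.

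**Inputs for the fibrosis scores.** Arm sizes 28 and 14 come from section 8.2 and alpha 0.05 from section 8.3; a two-sided test is taken. The standardized change dz (mean change divided by the SD of change) is an assumption. It is set equal in both arms, so exercise adds nothing.

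**Formula.** In an arm of size n, the paired t statistic is noncentral t with n − 1 df and noncentrality dz·√n. Write pE and pC for the rejection probabilities in the exercise and control arms. The arms are independent, so P(exercise only) = pE(1 − pC) and P(control only) = pC(1 − pE).

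Example at dz = 0.5: the noncentrality is 0.5·√28 = 2.65 and 0.5·√14 = 1.87, giving pE = 0.723 and pC = 0.410. Exercise only = 0.723 × 0.590 ≈ 0.43; control only = 0.410 × 0.277 ≈ 0.11.

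| dz, same in both arms | Exercise, n=28 | Control, n=14 | Exercise only | Control only |
|---|---|---|---|---|
| 0 | 5.0% | 5.0% | 4.8% | 4.8% |
| 0.2 | 17.5% | 10.7% | 15.7% | 8.8% |
| 0.3 | 33.4% | 18.0% | 27.4% | 12.0% |
| 0.4 | 53.2% | 28.4% | 38.1% | 13.3% |
| 0.5 | 72.3% | 41.0% | 42.6% | 11.4% |
| 0.6 | 86.4% | 54.7% | 39.2% | 7.4% |

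**With attrition.** At 22/11 and dz = 0.5 the arm-wise probabilities are 61% and 32%, with exercise only 41% and control only 13%. The pattern barely moves.

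**Between-arm alternative.** A two-sample t-test on change has noncentrality d/√(1/n₁ + 1/n₂), where d is the between-arm difference in SDs of change. If both arms change equally, d = 0 and the test rejects 5% of the time whatever the size of the common change. At 28/14, √(1/28 + 1/14) = 0.327, and power is 32% at d = 0.5, 67% at 0.8 and 85% at 1.0; 80% power needs d of about 0.94. At 22/11 the three powers are 26%, 56% and 75%.

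**The case against.** The strongest reply is that section 8.3 may already provide the between-arm test. NFS and FIB-4 are built from laboratory values, section 7.2 itself calls them serologic scoring systems, and the sentence before the paired-test sentence covers numerical laboratory data without exclusion. The paired-test sentence is qualified and gives an example; it does not say that this test is the only one, that it is run within each arm, or that it supports a treatment claim.

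Much of this stands. A reader might infer that the plan sets the control group aside for these scores, or that its two-sample tests are meant for other laboratory data only. The text says neither. What remains is that the scores are named only for the paired test. If both sentences apply, two tests answering different questions are planned with no stated precedence.

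The second reply concerns mechanism. Equal change in both arms is an assumption, not a prediction of the documents. Counseling is listed for all who consent, but section 7.2 describes the control condition as usual care with printed information, places the weekly dietary feedback in the exercise-condition text, and section 1.2 treats nutritional counseling as part of the program. This limits how far the probabilities can be pressed. It does not remove the problem, since some common change is plausible: section 7.2 allows that controls may take up exercise after reading the information, though it expects only small effects.

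The third reply, that these are exploratory measures, is correct and limits the severity.

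**Conclusion.** The point holds as a gap in specification with a limited consequence. Section 8.3 offers a pre/post paired test as its example for NFS and FIB-4 and does not explicitly give them a between-arm contrast. On any reading, that paired test cannot attribute a change to exercise.

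The imbalance in favor of the exercise arm is conditional. It needs arm-by-arm testing and a real change in both arms. For an assumed common change of 0.2 to 0.6 SD, significance in the exercise arm alone has probability of about 16% to 43%, against about 7% to 13% for the control arm alone. At 0.2 SD the gap is small (16% against 9%), and with no change it vanishes.

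A reader might go on to infer that the trial's main conclusion, or its other markers, are exposed to the same problem. The documents do not support that. The primary PAI-1 comparison is powered as a two-sample test, NFS and FIB-4 are not listed endpoints, and the paired-test sentence gives only fibrosis parameters as its example. The change is worth making because it is nearly free, not because the primary result depends on it.

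**What to change.** In section 8.3, state that end-of-program NFS and FIB-4 will be compared between the randomized arms by ANCOVA with the baseline score as covariate, reported as an adjusted difference with a 95% confidence interval. Add that within-arm pre/post changes are descriptive and will not be taken as evidence of an exercise effect.

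The cost is a sentence or two. The laboratories are already scheduled at Day 0 and Week 20, so no visit or sample is added. The downside is modest power: about 67% for a 0.8 SD between-arm difference in a t-test on change at 28/14, and 56% at 22/11. ANCOVA may improve on this, depending on the correlation between baseline and follow-up, which the documents do not give. For an exploratory outcome that is acceptable, and the confidence interval will show how much the data can say.
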